9.5 VITAL SIGNS ANALYSES

Descriptive statistics will be provided for the vital signs measurements for the SAF set by treatment cycle, as well as for the change from baseline. The baseline value is defined as the last non-missing value before the initial administration of study treatment. In addition, mean change from baseline will be presented for the maximum and minimum post-baseline values and the values at the End of Treatment visit (or the last value obtained under treatment).

A data listing will display all vital sign test results and findings.

9.6 ELECTROCARDIOGRAM ANALYSES

Descriptive statistics will be provided for the central ECG measurements for the SAF set by scheduled measurement times, as well as for the change from baseline. The baseline value is defined as the last non-missing value before the initial administration of study treatment. For triplicate measurements the mean value will be used for analysis. Based on NCI-CTCAE criteria, the number and percentage of patients with QTcF interval values less than or equal to 450, between 451 and 480, between 481 and 500, as well as >500 ms will be tabulated and changes from baseline of less than 30 ms, 30-60 ms and >60 ms, by treatment cycle and over all post treatment evaluations (worst value) will be summarized and described in relation to baseline values.

Along with QTcF interval also JTcF interval will be assessed and will be reported by scheduled measurements times, as well as for the change from baseline. JTcF takes into account the physiologic shortening of the JT interval which occurs as the heart rate increases, permitting comparison of the JT interval across a range of rates. It is mathematically defined as:

$$JTcF \text{ (msec)} = \frac{JT}{RR^{\frac{1}{3}}} \text{ (msec)},$$

where JT is defined as $JT \text{ (msec)} = QT - QRS \text{ (msec)}$. JTcF will be derived from ECG parameters following the formula above.

A data listing will display all ECG results and findings.

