| 
(non-binding). Proportionality of hazards is assumed. Assuming that median OS is 10.0 months in the Group B (placebo + AZA) the aim is to detect, by means of the log-rank test or equivalent, an increase to 14.0 months in Group A (pracinostat + AZA), i.e., a HR of 0.714. A total of 390 events (deaths) allows to meet a power requirement of at least 90% (actually 90.78%) at a study-wise one-sided significance level of 0.025.
 
Interim Analysis:
 
An interim analysis at 67% (2/3) of information (260 over 390 events (deaths), being the study event-driven) will be performed for both futility and superiority.
 
Statistical Evaluation:
 
Summary statistics for continuous variables will include the mean, standard deviation, median and range (minimum/maximum). Categorical variables will be presented as frequency counts and percentages, and time-to-event variables will be summarized using Kaplan-Meier estimates including median with 95% CI, number of events, number censored. Data listings will be created to support each table and to present all data.
 
The primary efficacy endpoint of overall survival will be analyzed using the intent-to-treat (ITT) set. Inferential statistical analysis for treatment group differences will be based on the stratified log-rank test at the $\alpha = 0.025$ level of significance (one-sided) including the stratification factors used for randomization. The unadjusted analysis will be performed as sensitivity analysis.
 
Secondary endpoints will be tested according to a fixed sequence method. If the primary endpoint is statistically significant, then the first secondary endpoint will be tested, and so on for the other three secondary endpoints. A group-sequential procedure will be applied also to the secondary endpoints.
 
Safety analyses will be performed on the Safety Set. Safety variables including treatment-emergent adverse events, laboratory tests, vital signs, and ECGs, will be summarized using appropriate descriptive statistics by treatment group.
 
The statistical analysis plan will provide full details of all planned analyses.
 |
|---|

LIST OF ABBREVIATIONS AND DEFINITIONS OF TERMS

| Abbreviation | Definition |
|--------------------|---|
| AE | Adverse Event |
| ALP | ALkaline Phosphatase |
| ALT | ALanine aminoTransferase |
| AML | Acute Myeloid Leukemia |
| ANC | Absolut Neuthrophils Count |
| Anti-HBc | Antibody against hepatitis B core antigen |

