4.2.2.2 Hematologic Symptoms

Pracinostat has been associated with myelosuppression including anemia, thrombocytopenia, and neutropenia (including neutropenic fever). Patients should be monitored for adverse hematologic effects, with dose modification allowed as described in Section 4.5.

Since myeloid malignancies may be characterized by thromboembolic events – including disseminated intravascular coagulation and hemorrhage – caution should be taken in concomitant administration of the following:

- Fibrinolysis inhibitors
- Anticoagulant and antiplatelet drugs

4.2.2.3 *Gastrointestinal Symptoms*

Disturbances of the GI tract, including nausea, vomiting, and diarrhea, have been reported in patients treated with pracinostat. In the Phase II study of pracinostat + AZA in AML, nausea, diarrhea and vomiting were among the most frequently reported manifestations of GI toxicity, with most cases graded as 1 or 2. Standard antiemetic and antidiarrheal medications and appropriate supportive care should be used per normal clinical practice. Pre-existing nausea, vomiting, and diarrhea should be adequately controlled before starting study drug administration.

4.2.2.4 *QTc Prolongation/Cardiac Events*

The cardiac safety of pracinostat compared to placebo on the QTcF or the individually corrected QT interval (QTcI) was assessed in 43 healthy subjects in study MEI-010. Following single oral doses of 60 and 120 mg pracinostat, there were dose-proportional increases in HR and QTcF, with peak increases that did not correlate with C_{max} (6 and 24 hours postdose for HR and QTcF, respectively). No clinically meaningful effect on PR or QRS intervals or on T-wave morphologies was noted.

Patients with a prolonged QTcF interval > 450 ms at Screening will not be permitted to participate in the study.

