6.2.2 Vital Signs

Vital signs assessments will include: pulse rate, systolic and diastolic blood pressure, body temperature, body weight, and height (at screening only).

Pulse rate, systolic and diastolic blood pressure will be measured after the patient has been in the sitting or in semi-supine position for at least 5 minutes. Measurements are done at Screening, on Day 1 of Cycle 1 (predose and 90 ±30 minutes postdose), on Day 15 of Cycle 1 (90 ±30 minutes postdose) on Day 1 of Cycle 2 (predose and 90 ±30 minutes postdose), at any time during the visit between Day 21 and Day 26 of Cycle 2 and 90 ±30 minutes postdose on Day 1 of all subsequent Cycles. Additionally these parameters are measured also during Drug Holiday Commencement and Follow-up Visits, as well as at End of Treatment Visit.

Body temperature is measured at Screening, on Day 1 of Cycle 1 (predose), on Day 15 of Cycle 1, on Day 1 of all subsequent Cycles (predose), as well as during Drug Holiday Commencement and Follow-up Visits, and at End of Treatment Visit.

Body weight is measured at Screening, on Day 1 of all Cycles, as well as during Drug Holiday Commencement and Follow-up Visits, and at End of Treatment Visit.

6.2.3 12-lead ECG

Twelve-lead ECGs will be recorded for each patient as triplicates or as single 12-lead ECG, as indicated in Section 5.1.

All ECGs will be recorded after the patient has been in sitting or in semi-supine position for at least 5 minutes. Triplicate ECGs are to be collected at a distance of 5±2 minutes between the ECGs.

Triplicate 12-lead ECGs are collected at Screening, on Day 1 of Cycle 1 (predose, 90 ±30 minutes and 6 hours ±30 minutes post pracinostat/placebo administration), on Day 2 of Cycle 1 (at 24 hours ± 1 hour post pracinostat/placebo administration), on Day 3 of Cycle 1 (at 48 hours ± 1 hour after the first pracinostat dose), on Day 15 of Cycle 1 (90 ±30 minutes post pracinostat/placebo administration), on Day 1 of Cycle 2 (predose and 90 ±30 minutes post pracinostat/placebo administration), and at Day 21-26 of Cycle 2 (at any time).

Single 12-lead ECGs are collected 90 ±30 minutes post pracinostat/placebo administration on Day 1 of each subsequent Odd cycle (i.e., Cycles 3, 5, 7 ...).

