9.8.4 Electrocardiogram Analyses

Descriptive statistics will be provided for the central ECG measurements by scheduled time of evaluation for the Safety set, as well as for the change from baseline. The baseline value is defined as the last non-missing value before the initial administration of study treatment. For triplicate measurements the mean value will be used for analysis. ECG abnormalities will be graded according to the CTCAE criteria. The number and percentage of patients with QTcF interval values less than or equal to 450, between 451 and 480, between 481 and 500, as well as >500 ms will be tabulated and changes from baseline of less than 30 ms, 30-60 ms and >60 ms over all post treatment evaluations and by cycle will be summarized and described in relation to baseline values. ECG data will also be presented in the data listings.

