5.6 STATISTICAL NOTATION AND METHODOLOGY

Summary statistics for continuous variables will include the mean, standard deviation, minimum, first quartile (Q1), median, third quartile (Q3), and maximum. Categorical

variables will be presented as frequency counts and percentages, and time-to-event variables will be summarized using Kaplan-Meier estimates including median with 95% CI, number of events, number censored.

In general, frequency tables will be presented by treatment group and overall except for efficacy analysis or otherwise specified.

Data listings will be created to support each table and to present all data.

Means, LS means, medians, and quartiles will be rounded to 1 decimal place greater than the precision of the original value, while standard deviations and SEs will be rounded to 2 decimal places greater than the precision of the original value. Percentages for summarizing categorical data will be rounded to one decimal place.

P-values will be presented with 4 decimal places and values less than 0.0001 will be presented as < 0.0001 .

Unless otherwise noted, all data collected during the study will be included in data listings and will be sorted by treatment group, patient number and then by visit or event as relevant. Additional details and sorting order for each listing are presented in section 14.

In case at least one parameter in a table has missing values, a row/column with the number of missing values will be added. In case no missing values are documented at all for a table, no missing rows/columns will be presented, even if missing rows/columns are foreseen in the respective table shell.

In case more than one unscheduled visits fall in the same visit window (screening/cycle) without a value at the scheduled visit, the latest value will be included in summary tables based on cycle.

The final decision whether the PP set is relevant to the study and if tables of baseline characteristics need to be produced for the PP set, will be made at the BDRM.

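### SAP 9.6 pre-specifies no pracinostat-minus-placebo QTcF difference or interval, although both arms have the matched ECGs needed to estimate one

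*SAP*

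**What the plan says.** - **Analysis.** SAP 9.6: "Descriptive statistics will be provided for the central ECG measurements for the SAF set by scheduled measurement times, as well as for the change from" pre-treatment baseline. Protocol 9.8.4 matches it: "Descriptive statistics will be provided for the central ECG measurements by scheduled time of evaluation for the Safety set". Both then count patients in QTcF bands (up to 450, 451-480, 481-500, above 500 ms) and in change bands (below 30, 30-60, above 60 ms). The SAP adds JTcF, summarised in the same descriptive way.
- **Unit.** "For triplicate measurements the mean value will be used for analysis" (SAP 9.6).
- **Display.** The protocol synopsis puts ECGs among the safety variables shown by arm: "ECGs, will be summarized using appropriate descriptive statistics by treatment group".
- **Meaning of descriptive.** SAP 5.6: "Summary statistics for continuous variables will include the mean, standard deviation, minimum, first quartile (Q1), median, third quartile (Q3), and maximum". Protocol 9.5 adds n. Neither gives an interval for a continuous variable.
- **Schedule.** Protocol 6.2.3: "Triplicate 12-lead ECGs are collected at Screening, on Day 1 of Cycle 1" (predose, 90 minutes, 6 hours). Further triplicates follow at 24 hours, at 48 hours, on Day 15 at 90 minutes, on Cycle 2 Day 1 (predose and 90 minutes) and once late in Cycle 2. Post-dose times run from intake of pracinostat or placebo, so both arms share one clock. A blinded cardiologist reads the ECGs centrally. From Cycle 3 there are only single ECGs, in odd cycles.
- **Prior signal.** Protocol 4.2.2.4, on single doses in healthy subjects: "there were dose-proportional increases in HR and QTcF" (HR here is heart rate). Heart rate peaked at 6 hours and QTcF at 24 hours, and the peaks did not track Cmax.

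**The concern.** QT prolongation is a named risk throughout the protocol. Section 4.5 lists it among reactions likely related to pracinostat. It sets an entry limit (3.4.1), a medication ban (4.7.3), hold rules (4.5.2) and mandatory AE reporting (8.2.6.1).

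A change from baseline within one arm is not a drug effect here. Both arms receive azacitidine and premedication for nausea (4.6.1). Appendix I lists several antiemetics as possible QT risks, and these may be used at the investigator's discretion. Section 4.2.2.4 itself warns about electrolyte disturbance. Subtracting the placebo arm removes these shared influences on average.

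The planned tables put two columns of means side by side and stop there. They do not state how large a drug effect the data show or leave open. The 24-hour QTcF peak makes a contrast by time point the natural summary, and the trial records a triplicate at that time in both arms.

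**Working it through.** **1. Is a contrast planned anywhere?** SAP 9.6 and protocol 9.8.4 name summaries, changes and band counts, but no model, difference or interval. SAP 5.6 defines continuous summaries without an interval. SAP 10 sends exposure-response work to a dedicated PK SAP, which is not among the documents. The summary table in SAP 13 covers efficacy only. So neither document pre-specifies a between-arm QTcF estimate.

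**2. Are the data there?** Yes, for Cycles 1 and 2: 1:1 allocation (protocol 9.2), one dose-timed triplicate schedule and blinded central reading (6.2.3).

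**3. How precise would the estimate be?** The documents give no sample size, margin or SD for QTcF, so there is no plan figure to reproduce.

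Inputs:
- Patients per arm: 500 planned (protocol 9.11), so 500 / 2 = 250. SAP 5.5 expects 85% recruited by the interim, and 0.85 × 500 / 2 is about 212, so 200 is a reasonable lower case. The 150 and 100 cases are assumptions that allow for missing or unusable ECGs.
- SD of the change in QTcF: assumed 15 to 25 ms.

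Formula: half-width of the two-sided 90% CI = 1.645 × SD × √(2/n).

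| n per arm | SD 15 ms | SD 20 ms | SD 25 ms |
|---|---|---|---|
| 250 | 2.21 | 2.94 | 3.68 |
| 200 | 2.47 | 3.29 | 4.11 |
| 150 | 2.85 | 3.80 | 4.75 |
| 100 | 3.49 | 4.65 | 5.82 |

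**4. What would that exclude?** The 5 and 10 ms benchmarks are illustrative, because the documents set no margin. The upper limit falls below a benchmark when the estimate is below benchmark minus half-width.
- n = 250, SD 15: estimate below 10 − 2.21 = 7.79 ms excludes 10 ms; below 5 − 2.21 = 2.79 ms excludes 5 ms.
- n = 200, SD 25: below 10 − 4.11 = 5.89 ms excludes 10 ms; below 5 − 4.11 = 0.89 ms excludes 5 ms.
- n = 100, SD 25: below 10 − 5.82 = 4.18 ms excludes 10 ms; 5 ms is excluded only if the estimate is negative (5 − 5.82 = −0.82 ms).

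If the true effect were 5 ms, the chance of excluding 10 ms is Φ(5/SE − 1.645) with SE = SD × √(2/n). This gives 0.98, 0.64 and 0.41 for the same three cases.

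**5. What does baseline adjustment add?** With an assumed correlation of 0.4 between baseline and change, the half-width is multiplied by √(1 − 0.4²) = 0.917, a cut of about 8%.

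**The case against.** The strongest reply is that the contrast can be recovered from what is planned. The tables give n, mean and SD of the change, by arm and by time, and the formula above needs nothing more. That is right. A reader might infer that the trial cannot tell an excluded QT effect from one that is merely not visible; the documents do not support that. What is missing is a pre-specified, baseline-adjusted estimate, and the adjustment itself gains only about 8% under the assumption above.

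Second, exposure-QTc work may be planned elsewhere. One might read SAP 10 as limiting the safety side to adverse events. It does say safety (AE) variables, but it does not say only, the PK endpoint refers to safety endpoints generally, and the PK SAP is unavailable. A concentration-QTc analysis cannot be ruled out. It would complement a randomised contrast at fixed times rather than replace it, particularly as the earlier peak did not track Cmax.

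Third, a dedicated QT study exists, with placebo and positive controls and doses of 60 and 120 mg. It used single doses in 43 healthy subjects, without azacitidine, so it narrows the gap without closing it. Nor can this trial be called the only randomised source in patients: protocol 3.3 mentions over 150 patients treated with the combination in 4 studies and does not describe every design.

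Fourth, QTc prolongation is already an event of special interest, tabulated by arm, and the outlier bands relate to the individual thresholds used for holds and AE reporting. That stands, but it answers a different question from the mean effect.

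**Conclusion.** The point holds as a modest, inexpensive improvement to a descriptive safety section. It is not an error or a contradiction, and it touches neither the primary analysis nor clinical management. The plan does not report a baseline-adjusted pracinostat-minus-placebo QTcF estimate with an interval, although the data for Cycles 1 and 2 are collected.

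With 200 to 250 patients per arm and an SD of 15 to 25 ms, the interval would be about ±2.2 to ±4.1 ms; with 100 per arm and SD 25 ms it would be ±5.8 ms. That is informative against a 10 ms effect. Against 5 ms it often is not, so the addition should not be presented as able to exclude an effect of that size. The SDs, the reduced patient counts and the correlation of 0.4 are assumptions. The time-matched triplicate contrast does not extend beyond Cycle 2.

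**What to change.** In SAP 9.6 add:
- For QTcF, JTcF and heart rate, the pracinostat-minus-placebo difference in change from the predose baseline at each Cycle 1 triplicate time (90 minutes, 6, 24 and 48 hours, Day 15) and on Cycle 2 Day 1. Use a linear model with treatment and baseline value, the triplicate mean as the unit, and a two-sided 90% CI.
- Between-arm risk differences with CIs for a change above 60 ms and for QTcF above 500 ms, stating the period covered, since time on treatment may differ between arms after Cycle 2.
- A statement that this is safety estimation without multiplicity control. SAP 11 places version 5 after unblinding of the interim results, so the addition should be dated as made after that point.

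The cost is one paragraph and one or two tables on data already collected, with no alpha spent and no extra ECGs. The drawback is several time points with unadjusted intervals, so an isolated interval excluding zero should not be over-read.

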9.7 PHYSICAL EXAMINATIONS

A data listing will display all physical examination results.

10 PHARMACOKINETIC ANALYSIS

The sparse concentration-time data collected for pracinostat and its metabolite will be analyzed by non-linear mixed effect modeling according to a population PK data analysis approach. The purpose of this analysis is to obtain exposure data in patients with AML, to characterize the PK parameters of pracinostat and its metabolite(s), and to identify relevant covariates affecting pracinostat exposure. In addition, exposure variables will be correlated to both efficacy and safety (AE) variables in a PK/PD analysis. The possible drug interaction of

Pracinostat on the PK of AZA will be evaluated by comparing the descriptive statistics of PK parameters of azacitidine in the two groups.

Details on the PK/PD methods and analysis and of the PK set(s) are provided in a dedicated SAP.

11 CHANGES TO THE PLANNED ANALYSES IN THE PROTOCOL

Version 2 of SAP was based on protocol version 3. The version 3 of the SAP reflects changes due to study protocol version 5. Version 4 of the SAP reflects minor changes needed to be implemented after the first dry-run of the data (before the Interim Analysis) and tuning of the rules for the new AML therapy. Version 5 of the SAP reflects changes decided before and during the BDRM for Final Analysis (after unblinding of the results of the Interim Analysis). Due to FDA request the following changes were applied in the SAP, which are not reflected in the study protocol:

- 1) Change of the function for performing the superiority test according to a group sequential design for the primary endpoint as requested by FDA
- 2) Change of the parameter of the function for performing the futility test according to a group sequential design for the primary endpoint, in order to maintain the same probabilities to stop for true and wrong futility
- 3) Change of the method to test for secondary endpoints to overcome some possible issues reported by FDA. The new proposal by Helsinn is under further review of FDA
- 4) Details on the interceding therapies have been included
- 5) Imputation rules for interceding therapies have been included

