4.4 PER PROTOCOL (PP)

This set will comprise patients who meet all eligibility criteria and receive randomized study treatment (i.e. study drug and AZA) without major deviations or violations. This set will be the secondary set analyzed for the efficacy endpoint OS.

Membership in above defined sets, especially in the PP set, will be determined prior to unblinding.

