6.1.2 Non-Date Values

Quality of life

Missing values will be managed according to EORTC QLQ-C30 version 3.0 manual (see reference 1 for further information).

According to this manual, scores of scales involving missing items will be computed only if at least half of the items from the scale have been answered. The scale score will be calculated by using all the items that were completed (any items with missing values will be ignored). If more than half of the items are missing (or the missing item is a single question) than the scale score will be set to missing. This will be independently applied to the calculation of each scale score (global scale score, functional scale scores, symptom scale scores)

As the analysis of the quality of life data are descriptive, no additional efforts are made to impute missing items. Especially completely missing forms will not be imputed.

Transfusion independence

In the case of missing transfusion dates no imputation will be done. However, the patient is counted as transfusion independent, if a duration of 56 days or more is calculated for two consecutive transfusions with non-missing dates. For the remaining patients with missing or incomplete transfusion dates the patient is regarded as not transfusion independent, but the final decision about transfusion independence will be taken at the BDRM, using a conservative approach.

Other non-date values

Other non-date values will not be inputted in any of the analysis.

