7.6 PROTOCOL DEVIATIONS

Protocol deviations will be summarized by treatment group and category for the ITT set. Deviations will be classified as major or minor, with major deviations resulting in exclusion from the Per Protocol set. Deviations referring to assessment of the disease might have impact also on the inclusion into the EE sets. The final decision whether a protocol deviation is major or minor and the assignment to the analysis sets is made at the BDRM.

A listing of all deviations will also be included. Included in the listing will be those protocol deviations coming from the PD tracker generated during study by the CRAs and those protocol deviations coming from the specific listings generated for the BDRM by programming.

For Covid19 related protocol deviations a separate listing will be provided.

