- The number of surviving patients, the number of deaths and the number of patients with censored values will be displayed as well.
- Censoring patterns will be examined between treatment groups. Therefore the censored and not censored observations in the two treatment groups will be analyzed over time in a scatterplot.
- The effect of subsequent therapy on OS will be analyzed, including an analysis that compares OS in the treatment groups with censoring at the start date of the new interceding therapy, including those started during study treatment phase (concomitant therapy) and after stopping of study treatment as recorded in the new AML therapy eCRF page. Balance of such cases in the two treatment groups will be assessed to evaluate the appropriateness of this analysis method.
- Other sensitivity analyses will be performed to assess the robustness of OS results, if relevant. These will be decided prior to unblinding (e.g. at BDRM) based on real data.
- The primary OS analysis (stratified log-rank test) will be repeated for the PP set.
- Impact on OS of other baseline/demographic factors (including those considered for the subgroup analysis (section 5.3), plus possible others), will not be evaluated by means of Cox PH model(s) as initially planned due to the evident lack of the PH assumption for the treatment group factor.

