13 SUMMARY OF PLANNED EFFICACY ANALYSES

At the BDRM it might be decided not to perform any analyses for the PP set (depending on the number of patients to be excluded from the ITT set) and to add analyses for sensitivity and / or additional subgroups.

Type of endpoint	Endpoint	Analysis set	Stratification	Test	Other feature	Relevance
primary	OS	ITT	ECOG, RISK (randomization)	Log-rank	none	Primary analysis for this endpoint
primary	OS	ITT	ECOG (Day 1 Cycle 1), RISK (centralized)	Log-rank	none	sensitivity
primary	OS	ITT	none	Log-rank	none	sensitivity
primary	OS	ITT	ECOG, RISK (randomization)	Cox PH	none	sensitivity
primary	OS	ITT	ECOG, RISK (randomization)	Log-rank	Censor at time of new therapy	sensitivity
primary	OS	PP	ECOG, RISK (randomization)	Log-rank	none	Secondary set
primary	OS	ITT	ECOG, RISK (randomization) + other factors	Cox PH	none	Exploratory Factors and related levels to be decided at BDRM
First secondary	CR	ITT	ECOG, RISK (randomization)	CMH	none	Primary analysis for this endpoint
First secondary	CR	EE-1	ECOG, RISK (randomization)	CMH	none	Secondary set
First secondary	CR	ITT	none	LRT	none	sensitivity
First secondary	CR	EE-1	none	LRT	none	Sensitivity on secondary set

First secondary	CR	ITT	ECOG, RISK (randomization) + other factors	Logistic regression	none	Exploratory Factors and related levels to be decided at BDRM
Second secondary	Transfusion independence	ITT	ECOG, RISK (randomization)	CMH	none	Primary analysis for this endpoint
Third secondary	CR _{M RD} -	ITT	ECOG, RISK (randomization)	CMH	none	Primary analysis for this endpoint
Third secondary	CR _{M RD} -	EE-1	ECOG, RISK (randomization)	CMH	none	Secondary set
Fourth secondary	CRc	ITT-2	ECOG, RISK (randomization)	CMH	none	Primary analysis for this endpoint
Fourth secondary	CRc	EE-2	ECOG, RISK (randomization)	CMH	none	Sensitivity on secondary set
Explorative	cCR	ITT	ECOG, RISK (randomization)	CMH	none	Primary analysis for this endpoint
Explorative	cCR	EE-1	ECOG, RISK (randomization)	CMH	none	Secondary set
Explorative	BR	ITT	none	none	none	Primary analysis for this endpoint
Explorative	BR	EE-1	none	none	none	Secondary analysis for this endpoint
Explorative	RFS	ITT	ECOG, RISK (randomization)	Log-rank	none	Primary analysis for this endpoint
Explorative	RFS	ITT	ECOG, RISK (randomization)	Log-rank	Censor at time of new therapy	sensitivity
Explorative	PFS	ITT	ECOG, RISK (randomization)	Log-rank	none	Primary analysis for this endpoint

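### SAP 4.4 and 8.1.2 promise that analysis sets and added survival analyses are settled before unblinding, but SAP 11 places the final data review after the interim results were unblinded

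*SAP*

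**What the plan says.** On timing, SAP 4.4 states: "Membership in above defined sets, especially in the PP set, will be determined prior to unblinding". On further OS sensitivity analyses, SAP 8.1.2 states: "These will be decided prior to unblinding (e.g. at BDRM) based on real data".

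On where the decisions are taken, SAP 7.6 states: "The final decision whether a protocol deviation is major or minor and the assignment to the analysis sets is made at the BDRM". SAP 13 adds "At the BDRM it might be decided not to perform any analyses for the PP set" and also allows the meeting "to add analyses for sensitivity and / or additional subgroups". For transfusion independence with missing or incomplete dates, SAP 6.1.2 says that "the final decision about transfusion independence will be taken at the BDRM, using a conservative approach".

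On what had happened by then, SAP 11 describes version 5 of the SAP as reflecting "changes decided before and during the BDRM for Final Analysis (after unblinding of the results of the Interim Analysis". SAP 8.1.2 says that Cox models of other baseline and demographic factors, planned in protocol 9.7.1, will not be run "due to the evident lack of the PH assumption for the treatment group factor".

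SAP 8.1.1 has the unblinded statistician at the CRO send the interim efficacy analyses to the IDMC, which then makes a recommendation to the sponsor.

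**The concern.** Settling sets and extra analyses at a blind review is meant to assure the reader that these choices were not influenced by how the arms compare. SAP 4.4 and 8.1.2 give that assurance. SAP 11 and the reason given for dropping the Cox models indicate that the comparison was known, at least in aggregate, when version 5 was written.

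At stake is the standing of the supporting analyses. If the report repeats the current wording, readers will treat the per-protocol (PP) result, the added sensitivity analyses and subgroups, and the residual transfusion calls as chosen in ignorance of the result. That gives them more weight than the documents justify.

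**Working it through.** No figure in the plan decides this point. It rests on comparing statements within the current SAP.

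**Step 1: the promise.** SAP 4.4 sets the time of set assignment (before unblinding) without naming a meeting. SAP 7.6 names the meeting (the BDRM). SAP 8.1.2 links the two for added OS sensitivity analyses.

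**Step 2: the date.** SAP 11 places the version 5 changes before and during the BDRM for the final analysis, and after the interim results were unblinded. I read the parenthesis as dating either the changes or the meeting; both readings give this order.

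**Step 3: did between-arm information reach the plan?** Whether the treatment hazard ratio is constant can be judged only from survival split by arm. SAP 8.1.1 planned such a display at the interim: log negative log survival for each treatment group within strata. The evident departure cited in SAP 8.1.2 therefore requires arm-level information, though not patient codes. SAP 11 does not itemise the version 5 changes. Its five numbered items are attributed to an FDA request, and the dropped Cox models are not among them.

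**Step 4: how informative is the interim?** Planned information is 260/390 = 0.667 (SAP 3.1). As a check on that fraction, O'Brien-Fleming-type spending gives 2[1 − Φ(2.2414/√0.667)] = 2[1 − Φ(2.745)] = 0.00605, the interim level in SAP 5.5. The interim and planned final log-rank statistics have correlation √(260/390) = 0.816. Knowing the interim result therefore reveals much of the planned final comparison. The actual information fraction is not given.

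**Step 5: what the meeting controls.**

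| Item | Left to the BDRM | Limits in the text |
|---|---|---|
| PP set | Major/minor calls and assignment (7.6); whether it is analysed (5.6, 13) | Secondary set for OS |
| EE-1, EE-2 | Assessment deviations might affect inclusion (7.6) | Defined by recorded data (4.3); secondary or sensitivity role (13) |
| Extra OS sensitivity analyses, subgroups | Open (8.1.2, 13) | Subgroup results exploratory (5.3) |
| Other covariates | Open (5.2) | None stated |
| Transfusion independence | Patients with missing or incomplete dates not already qualifying (6.1.2) | Default is not independent; others follow the algorithm in 8.2 |
| OS, CR and CR without MRD in ITT; CRc in ITT-2 | Not dependent on these membership calls | Exclusion of sites unable to assess MRD is a written rule (SAP 8.2, protocol 9.7.2.3) |

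**Step 6: size of the transfusion discretion.** Assuming the maximum of 500 patients, 1:1 allocation gives 250 per arm. Each call moves one arm's rate by 1/250 = 0.4 percentage points, so k calls in one arm move it by 0.4k points. The SAP gives no value for k.

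**Step 7: consistency.** SAP 13 still lists the exploratory Cox row with factors to be chosen at the BDRM, although SAP 8.1.2 removes that analysis.

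**The case against.** The strongest reply is that unblinding in SAP 4.4 and 8.1.2 means release of patient treatment codes for the final analysis. SAP 11 speaks only of interim results, and the meeting is still called blind. Non-proportional hazards can be seen in aggregate curves, so set decisions may have been made without codes. SAP 11 discloses the sequence openly. An earlier BDRM may also have taken place before the interim.

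Much of this stands. Several stronger readings are tempting, but the documents do not support them:

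- A reader might infer that those assigning patients to sets held treatment codes. Nothing says codes were released.
- A reader might infer that interim results passed improperly beyond the IDMC. The SAP does not say who saw them or why, or whether the trial stopped at the interim.
- A reader might infer that the meeting decides transfusion independence generally. SAP 6.1.2 limits it to the residual patients with missing or incomplete dates, asks for a conservative approach and supplies a default.
- A reader might want version 4 rules restored because that version preceded the interim. Version 4 is not among the documents, and nothing shows that version 5 changed a set or transfusion rule.

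The reply does not rescue the wording. Being blind to codes is not the same as being blind to the result, and choosing analyses on real data is vulnerable to knowing the result. The disclosure in SAP 11 does not correct the statements it contradicts. No passage says that membership was locked at an earlier meeting.

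**Conclusion.** The point holds as a contradiction within the current SAP about when decisions were made. The statements in 4.4 and 8.1.2 cannot be read as meaning blind to the treatment comparison, because 11 and 8.1.2 together show that between-arm information had reached the plan. Whether patient-level calls were blind to codes remains open.

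The size is moderate and not numeric. A reader might infer that the primary result is compromised; it is not, because the stratified log-rank test uses all randomized patients. The main analyses of CR, CR without MRD and CRc likewise do not turn on these membership calls. The exposed items are the PP set, EE membership at the margin, the choice of added analyses, and the residual transfusion calls. The last matter most formally, because transfusion independence is second in the secondary testing sequence (SAP 5.4), although it is reached only if OS and then CR are significant.

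The consequence also depends on something the documents do not state. If the trial stopped at the interim, SAP 8.1.2 makes these analyses and the secondary endpoints exploratory, so the confirmatory harm largely disappears. The inaccurate description of timing would remain.

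**What to change.** 1. Reword SAP 4.4 and 8.1.2 to the true sequence. State who was unblinded, when, and whether to aggregate results or to patient codes.
2. In SAP 11, list every version 5 change and mark it as made before or after interim unblinding. Include the dropped Cox models.
3. In the tables, label post-interim changes and every analysis added at the BDRM as post hoc.
4. For transfusion independence, make the written 6.1.2 default the main rule: remaining patients with missing or incomplete dates count as not independent. Show any BDRM override only as a sensitivity analysis.
5. Align the exploratory Cox row in SAP 13 with SAP 8.1.2.

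The cost is SAP wording, table labels and possibly one extra transfusion table; no new data are needed. The downside is that some added analyses lose their pre-specified label, and a patient whom the meeting would have judged independent counts as not independent in the main analysis.
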